#### 9.4.5. Pharmacokinetic/Pharmacodynamic Analyses

Analyses of the PK of mirikizumab and relationships between exposure and the efficacy endpoints will be conducted.

The PK of mirikizumab will be characterized using graphical evaluations. The observed serum concentration data will be overlaid to the PK profile of adult patients with CD at the same dose for a comparison.

CC1

Population PK modeling and model-based analysis for exposure response relationship may be conducted if deemed appropriate. Data from this study may be combined with other study data, if appropriate, for the modeling analysis.

[figure not shown]
#### 9.4.6. Evaluation of Immunogenicity

Frequencies and percentages will be tabulated for the following:

- CCI
- CCI

CC1

 additional details will be provided in the addendum SAP.

#### 9.4.7. Other Analyses

CC1

CC1

##### 9.4.7.2. Subgroup Analyses

Subgroup analyses may be conducted for the coprimary and selected secondary endpoints. Subgroups to be evaluated may include sex, age, body weight, race, ethnicity, geographic region, baseline SES-CD category, baseline AP/SF category, corticosteroid use at baseline, duration of

disease, and disease location. A detailed description of the subgroup variables and analyses will be provided in the addendum SAP.

This study is not powered for subgroup analyses; therefore, all subgroup analyses will be treated as exploratory.

Analyses specifically requested by regulatory agencies will be identified as appropriate.

## **9.5. Interim Analyses**

Adolescent pharmacokinetic (PK) and safety data from Study AMAM will be needed to inform dosing decisions for other pediatric mirikizumab trials. To accomplish this, a snapshot of the PK and safety data (including AEs, labs, and vital signs) will be taken of the adolescent patients when approximately **CCI** [REDACTED]. If the adolescent PK exposure models are inconsistent with previous adult PK exposure models, a second PK snapshot may be performed if more information is needed to sufficiently determine drug exposure in adolescent patients. The timing of the second snapshot will be based on how much information is still needed after the first snapshot. Additional details on the analysis are found in the PK/pharmacodynamic (PD) analysis plan.

A DMC consisting of members external to Lilly will be established for interim safety monitoring across all the sponsor's Phase 3 studies in patients with CD, as well as a specific Pediatric IBD DMC, also composed of members external to Lilly. See Appendix [10.1.4](#) for more information. Unblinding details can be found in the unblinding plan. Analysis details can be found in the Population PK/PD Analysis Plan.

## **10. Supporting Documentation and Operational Considerations**

### **10.1. Appendix 1: Regulatory, Ethical, and Study Oversight Considerations**

#### **10.1.1. Regulatory and Ethical Considerations**

This study will be conducted in accordance with the protocol and with the following:

- Consensus ethical principles derived from international guidelines including the Declaration of Helsinki and Council for International Organizations of Medical Sciences (CIOMS) International Ethical Guidelines
- Applicable International Council for Harmonisation (ICH) GCP Guidelines
- Applicable laws and regulations

The protocol, protocol amendments and addenda, ICF(s), IB, and other relevant documents (for example, advertisements) must be submitted to an IRB/IEC by the investigator and reviewed and approved by the IRB/IEC before the study is initiated.

Any amendments to the protocol will require IRB/IEC approval before implementation of changes made to the study design, except for changes necessary to eliminate an immediate hazard to study participants.

The investigator will be responsible for the following:

- Providing written summaries of the status of the study to the IRB/IEC annually or more frequently in accordance with the requirements, policies, and procedures established by the IRB/IEC.
- Notifying the IRB/IEC of SAEs or other significant safety findings as required by IRB/IEC procedures.
- Providing oversight of the conduct of the study at the site and adherence to requirements of 21 CFR, ICH guidelines, the IRB/IEC, European regulation 536/2014 for clinical studies (if applicable), and all other applicable local regulations.
- Reporting cases of suspected child abuse and/or neglect according to local medical association (e.g., [American Academy of Pediatrics (AAP)] or health department guidelines].

After reading the protocol, each principal investigator will sign the separate protocol signature page and send a copy of the signed page to a Lilly representative.

#### **10.1.2. Informed Consent Process**

The investigator or his or her representative will explain the nature of the study to the participant or his or her legally authorized representative, explain the risks and benefits of participating in the study, and answer all questions regarding the study.

Participants must be informed that their participation is voluntary.

Participants or their legally authorized representative defined as parent/legal guardian will be required to sign a statement of informed consent that meets the requirements of 21 CFR 50; local regulations; ICH guidelines; Health Insurance Portability and Accountability Act (HIPAA) requirements, where applicable; and the IRB/IEC or study center.

The medical record must include a statement that legally authorized representative (parent/legal guardian) consent and adolescent assent (if deemed appropriate by local ethics review) was obtained before the participant was enrolled in the study and the date the written consent was obtained. The medical record should also describe how the clinical investigator determined that the person signing the ICF was the participant's legally authorized representative (parent/legal guardian). The authorized person obtaining the informed consent must also sign the ICF(s).

Participants and their legally authorized representative (parent/legal guardian) must be re-consented and re-assented to the most current version of the ICF(s) during their participation in the study.

Minor participants must be reconsented if they reach the age of majority during the course of the study, in order to continue participating.

A copy of the ICF(s) must be provided to the participant or the participant's parent/legal guardian. A copy of the ICF(s) is kept on file.

Participants who are rescreened are required to sign a new ICF. A copy of the ICF(s) must be provided to the participant or the participant's parent/legal guardian. Obtain informed consent for continued participation from pediatric participants once a child reaches the age of legal consent.

#### **10.1.3. Data Protection**

Participants will be assigned a unique identifier by the investigator. Any participant records or datasets that are transferred to the sponsor will contain the identifier only; participant names or any information which would make the participant identifiable will not be transferred.

The participant must be informed that his/her personal study-related data will be used by the sponsor in accordance with local data protection law. The level of disclosure must also be explained to the participant.

The participant must be informed that his or her medical records may be examined by Clinical Quality Assurance auditors or other authorized personnel appointed by the sponsor, by appropriate IRB/IEC members, and by inspectors from regulatory authorities.

#### **10.1.4. Committees Structure**

CCI

##### Data Monitoring Committee

A DMC consisting of members external to Lilly will be established. The purpose of the DMC is to conduct periodic monitoring of clinical trial data for the Phase 3 CD program. The DMC will consist of a minimum of 5 members, including a physician with expertise in gastroenterology, pediatrics, and a statistician.

No member of the DMC will have contact with study sites. A statistical analysis center (SAC) will prepare and provide unblinded data to the DMC. The SAC members may be Lilly employees or from third-party organizations designated by Lilly. The SAC members will be external to the study team and will have no contact with sites and no privileges to influence changes to the ongoing studies. The timing and frequency of the periodic clinical trial data review by the DMC will be detailed in a DMC charter.

The DMC is authorized to evaluate unblinded interim efficacy and safety analyses. In addition, the DMC may request key efficacy data to put safety observations into context and to assess a reasonable benefit/risk profile for ongoing patients in the study. The DMC will make recommendation to the Lilly Research Laboratories Senior Management Designee, who may order the immediate implementation of the DMC recommendation, or may convene an internal review committee (IRC), which is independent from the study team, to review the recommendation according to standard Lilly policy. Study sites will receive information about interim results ONLY if it is required for the safety of their patients.

#### **10.1.5. Dissemination of Clinical Study Data**

##### Report Preparation

The CSR coordinating investigator will sign the final CSR for this study, indicating agreement that, to the best of his or her knowledge, the report accurately describes the conduct and results of the study.

##### Public Access to Reports and Data

###### *Reports*

The sponsor will disclose a summary of study information, including tabular study results, on publicly available websites where required by local law or regulation.

###### *Data*

The sponsor provides access to all individual participant data collected during the trial, after anonymization, with the exception of pharmacokinetic or genetic data. Data are available to request 6 months after the indication studied has been approved in the US and EU and after primary publication acceptance, whichever is later. No expiration date of data requests is currently set once they are made available. Access is provided after a proposal has been approved by an independent review committee identified for this purpose and after receipt of a signed data sharing agreement. Data and documents, including the study protocol, SAP, clinical study report, blank or annotated case report forms (CRFs), will be provided in a secure data sharing environment for up to 2 years per proposal. For details on submitting a request, see the instructions provided at [www.clinicalstudydatarequest.com](http://www.clinicalstudydatarequest.com).

###### Publications

For policies on publications, see Section [10.1.9](#).

### 10.1.6. Data Quality Assurance

To ensure accurate, complete, and reliable data, Lilly or its representatives will do the following:

- provide instructional material to the study sites, as appropriate
- provide sponsor start-up training to instruct the investigators and study coordinators. This training will give instruction on the protocol, the completion of the eCRFs, and study procedures.
- make periodic visits to the study site
- be available for consultation and stay in contact with the study site personnel by mail, telephone, and/or fax
- review and verify data reported to detect potential errors

In addition, Lilly or its representatives will periodically check a sample of the participant data recorded against source documents at the study site. The study may be audited by Lilly or its representatives and/or regulatory agencies at any time. Investigators will be given notice before an audit occurs.

The investigator will keep records of all original source data. This might include laboratory tests, medical records, and clinical notes. If requested, the investigator will provide the sponsor, applicable regulatory agencies, and applicable ERBs with direct access to original source documents.

### Data Capture System

The investigator is responsible for ensuring the accuracy, completeness, legibility, and timeliness of the data reported to the sponsor.

An electronic data capture system (EDC) will be used in this study for the collection of eCRF data. The investigator maintains a separate source for the data entered by the investigator or designee into the sponsor-provided EDC system. The investigator is responsible for the identification of any data to be considered source and for the confirmation that data reported are accurate and complete by signing the eCRF.

Additionally, clinical outcome assessment (COA) data (questionnaires) will be collected by the investigator site personnel, via a paper source document and will be transcribed by the investigator site personnel into the EDC system.

CCI

A large rectangular area of the page is completely blacked out, indicating redacted content. The text 'CCI' is visible in red at the top left corner of this redacted area.

Data collected via the sponsor-provided data capture systems will be stored at third parties. The investigator will have continuous access to the data during the study and until decommissioning of the data capture systems. Prior to decommissioning, the investigator will receive an archival copy of pertinent data for retention.

Data managed by a central vendor, such as laboratory test data, will be stored electronically in the central vendor's database system and electronic transfers will be provided to the investigator for review and retention. Data will subsequently be transferred from the central vendor to the Lilly data warehouse.

Data from complaint forms submitted to Lilly will be encoded and stored in the global product complaint management system.

#### **10.1.7. Source Documents**

Source documents provide evidence for the existence of the participant and substantiate the integrity of the data collected. Source documents are filed at the investigator's site.

Data reported on the eCRF or entered in the eCRF that are transcribed from source documents must be consistent with the source documents or the discrepancies must be explained. The investigator may need to request previous medical records or transfer records, depending on the study. Also, current medical records must be available.

What constitutes source data is described in Section [10.1.6](#).

#### **10.1.8. Study and Site Closure**

##### **10.1.8.1. Discontinuation of the Study**

The study will be discontinued if Lilly or its designee judges it necessary for medical, safety, regulatory, or other reasons consistent with applicable laws, regulations, and GCP.

##### **10.1.8.2. Discontinuation of Study Sites**

Study site participation may be discontinued if Lilly or its designee, the investigator, or the ERB of the study site judges it necessary for medical, safety, regulatory, or other reasons consistent with applicable laws, regulations, and GCP.

#### **10.1.9. Publication Policy**

[figure not shown]
The publication policy is described in the letters of agreement between the sponsor and the investigators and institutions.

## 10.2. Appendix 2: Clinical Laboratory Tests

## Clinical Laboratory Tests

CCI

## 10.4. Appendix 4: Risk Factors for Latent Tuberculosis Infection

Risk Factors for Latent Tuberculosis Infection (LTBI)
Household contact or recent exposure to an active case
Birth or residency in a high burden country (>20/100,000)
Residents and employees of high risk congregate settings, for example, prisons, homelessness, intravenous drug use

Source: adapted from Horsburgh and Rubin 2011 and Lewinsohn et al. 2017.

Risk Factors for Increased Likelihood of Progression from LTBI to Active TB
Household contact or close contact with an active case
HIV
Radiographic evidence of old, healed TB that was not treated
Silicosis
Treatment with $\geq 15$ mg prednisone (or equivalent) per day
Children $<5$ years of age
Chronic renal failure
Treatment with an anti-TNF antibody
Poorly controlled diabetes
Intravenous drug use
Weight $\geq 10\%$ below normal
Smoking

Abbreviations: HIV = human immunodeficiency virus; LTBI = latent tuberculosis infection; TB = tuberculosis; TNF = tumor necrosis factor.

Source: adapted from Horsburgh and Rubin 2011.

World Health Organization List of High Burden Countries		
Angola	India	Peru
Azerbaijan	Indonesia	Philippines
Bangladesh	Kenya	Russian Federation
Belarus	Kazakhstan	Sierra Leone
Botswana	Democratic People's Republic of Korea	Somalia
Brazil	Kyrgyzstan	South Africa
Cambodia	Lesotho	Swaziland
Cameroon	Liberia	Tajikistan
Central African Republic	Malawi	United Republic of Tanzania
Chad	Republic of Moldova	Thailand
China	Mozambique	Uganda
Congo	Myanmar	Ukraine
Democratic Republic of the Congo	Namibia	Uzbekistan
Ethiopia	Nigeria	Vietnam
Ghana	Pakistan	Zambia
Guinea-Bissau	Papua New Guinea	Zimbabwe

Source: WHO 2015

### **10.5. Appendix 5: Examples of Infections that May Be Considered Opportunistic in the Setting of Biologic Therapy**

This table is provided to aid the investigator in recognizing infections that may be considered opportunistic in the context of biologic therapy, for the purposes of exclusion criteria. This list is not exhaustive. Investigators should use their own clinical judgement in determining if other infections may be considered opportunistic, for the purposes of exclusion criteria. Winthrop et al. (2015) consider TB and non-TB mycobacterial disease to be opportunistic infections in the context of biologic therapy.

Bacterial
Bartonellosis (disseminated disease only)
Campylobacteriosis (invasive disease only)
Legionellosis
Listeriosis (invasive disease only)
Nocardiosis
Tuberculosis
Nontuberculous mycobacterial disease
Salmonellosis (invasive disease only)
Shigellosis (invasive disease only)
Vibriosis (invasive disease due to Vibrio vulnificus )
Viral
BK virus disease including polyomavirus-associated nephropathy
Cytomegalovirus disease
Hepatitis B virus reactivation
Hepatitis C virus progression
Herpes simplex (invasive disease only)
Herpes zoster (any form)
Post-transplant lymphoproliferative disorder (Epstein-Barr virus)
Progressive multifocal leukoencephalopathy (PML), John Cunningham (JC) virus
Fungal
Aspergillosis (invasive disease only)
Blastomycosis
Candidiasis (invasive disease or oropharyngeal, esophageal. Not isolated lingual)
Coccidioidomycosis
Cryptococcosis
Histoplasmosis
Paracoccidioides infections
Penicilliosis
Pneumocystosis
Sporotrichosis
Other invasive molds: Mucormycosis (zygomycosis) ( Rhizopus , Mucor , and Lichtheimia ), Scedosporium/Pseudallescheria boydii , Fusarium
Parasites
Leishmaniasis (visceral only)
Strongyloidosis (hyperinfection syndrome or disseminated disease)
Microsporidiosis
Toxoplasmosis
Trypanosoma cruzi infection (Chagas' disease progression) (disseminated disease only)
Cryptosporidiosis (chronic disease only)

Source: Adapted from Winthrop et al. 2015.

## 10.6. Appendix 6: Prohibited Medications

This section outlines medications that are prohibited during the treatment phase of the study and during washout periods prior to the screening endoscopy, if applicable. Use of the medications listed in this appendix is allowed at the discretion of the investigator after a participant discontinues study drug and completes the ETV.

Drug Class	Guidance for Use
Anti-TNF antibodies (for example, infliximab, adalimumab, or certolizumab pegol)	CCI
Anti-integrin antibodies:  natalizumab	CCI
Agents depleting B or T cells (for example, rituximab, alemtuzumab, or visilizumab)	CCI
Immunomodulatory medications, including oral cyclosporine, IV cyclosporine, tacrolimus, mycophenolate mofetil thalidomide, or JAK inhibitors	CCI
Rectally administered 5-ASA therapies (enemas or suppositories)	CCI
Rectally administered corticosteroids (enemas or suppositories)	CCI
IV corticosteroids	CCI

Drug Class	Guidance for Use
Systemic corticosteroids for non-CD indications (oral or IV)	CCI
Any biologic investigational therapy	
Any nonbiologic investigational therapy	
Interferon therapy	
Leukocyte apheresis (leukapheresis, for example, Adacolumn)	
Anti-IL-23p19 antibodies (for example, risankizumab [BI-655066], brazikumab [MEDI-2070], guselkumab [CANTO1959], tildrakizumab [MK-3222]) for any indication, including investigational use	
Anti-IL 12/23p40 antibodies (for example, ustekinumab)	
Bacillus Calmette-Guerin (BCG) and live attenuated vaccines	
Medicinal and recreational marijuana (includes CDB oil)	

Abbreviations: 5-ASA = 5-aminosalicylic acid; CBD = cannabidiol; CD = Crohn's disease; IL = interleukin; IV = intravenous; JAK = Janus kinase; TNF= tumor necrosis factor.

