## 4. Study Design

### 4.1. Overall Design

#### Design Summary

This open-label addendum to the AMAM adult study will assess efficacy and safety of mirikizumab in the induction and maintenance of remission in adolescents (15 to <18 years of age) with moderately to severely active Crohn's Disease. See Schema in Section 1.2.

Addendum participants with moderate-to-severe CD will be unblinded to treatment for the full duration of the study, though the study material assigned and dispensed has blinded labeling (Section 6.3). During the induction period, participants will receive 900 mg mirikizumab by IV infusion doses at Weeks 0, 4, and 8. In the maintenance period, participants will receive 300 mg mirikizumab by SC injection every 4 weeks until Week 48.

Adult double-blind and double dummy placebo-treated participants will be used as the comparator for adolescent mirikizumab treated patients, noting:

- When Period 1 induction dosing concludes (Week 12), placebo responders continue receiving placebo, and placebo nonresponders (NRs) at Week 12 will receive mirikizumab as described in the adult protocol.

The total duration of the combined treatment periods is up to 52 weeks.

The maximum total duration of study participation for each participant, including screening and the post-treatment follow-up period, is 73 weeks.

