### Vaccinations

During the screening period, the investigator must review the study participant's vaccine record to confirm required vaccinations are up to date. If nonlive vaccination is needed, it should be performed during the screening period prior to the first dose of study drug. Use of BCG vaccination is prohibited throughout the duration of the study and for **CCI** after discontinuation of study drug.

Use of live, attenuated vaccines is prohibited **CCI**

Use of nonlive (killed, inactivated, subunit and RNA-based) vaccinations is allowed; **CCI**

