### For More Information

The list of prohibited medications is provided in Appendix 10.6.

The list of permitted medications with dose stabilization guidance is provided in Appendix 10.7.

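### Appendix 6 and section 6.5.2 of the protocol give opposite instructions on BCG vaccination for a participant who has stopped study drug early and completed the early termination visit

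*Protocol*

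**What the plan says.** **Appendix 6 (protocol section 10.6).** The introduction describes the table as covering "medications that are prohibited during the treatment phase of the study", together with washout before the screening endoscopy. It then says that any product "listed in this appendix is allowed at the discretion of the investigator after a participant discontinues study drug and completes the ETV". One row of the table reads "Bacillus Calmette-Guerin (BCG) and live attenuated vaccines". The guidance cell for that row cannot be read.

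**Section 6.5.2, Vaccinations.** "Use of BCG vaccination is prohibited throughout the duration of the study and for" a redacted period "after discontinuation of study drug". The next rule begins "Use of live, attenuated vaccines is prohibited", and the rest of that sentence is redacted.

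**Cross-reference.** Directly after the vaccination text, the protocol tells sites: "The list of prohibited medications is provided in Appendix 10.6". It does not say which passage governs if the two differ.

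**What follows the ETV.** Sections 4.1 (Participant Visit Scheme) and 7.1 send participants who permanently stop drug early to an ETV and then to post-treatment follow-up visits. Section 4.1 (Design Summary) counts that follow-up as participation: "The maximum total duration of study participation for each participant, including screening and the post-treatment follow-up period, is 73 weeks". Section 6.7.1 likewise treats completing follow-up as the end of participation.

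**The concern.** A site with an early discontinuer who has just had the ETV can find two instructions on BCG in the same protocol. Appendix 6 leaves the vaccine to the investigator's judgement. Section 6.5.2 still bars it. A site that followed Appendix 6 literally would breach section 6.5.2, and neither the site nor the sponsor could say from the text whether a deviation had occurred. The appendix is also where section 6.5 directs sites for the list, so it is a likely page to be consulted.

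At stake is a clear participant-safety instruction for adolescents in follow-up. The efficacy results are not at stake.

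**Working it through.** No statistical figure is involved. The check sets the two rules side by side and asks whether a redacted item could remove the conflict.

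1. **Is BCG within the Appendix 6 permission?** The permission covers the medications listed in the appendix, without exception. BCG has a row there. Yes.
2. **When does the permission start?** It needs two events: study drug stopped and the ETV completed. The ETV belongs to early permanent discontinuation (sections 4.1 and 7.1).
3. **Is the participant still in the study then?** Follow-up visits come after the ETV, and follow-up is part of participation. Yes.
4. **What does section 6.5.2 say for that time?** It bars BCG for the whole study, and separately for a redacted period after drug is stopped. The first limb alone covers the interval from the ETV to the last follow-up visit.

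| Early discontinuer, after the ETV and before the last follow-up visit | BCG |
|---|---|
| Appendix 6, opening text | Allowed if the investigator judges it appropriate |
| Section 6.5.2, Vaccinations | Prohibited |

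5. **Does the redacted period matter?** No. Step 4 does not use it. A long period could only extend the conflict beyond the last visit.
6. **Does the redacted guidance cell matter?** If it repeats the general permission, the conflict is as shown. If it sets a restriction, the opening sentence disagrees with its own table as well as with section 6.5.2. Either way the wording needs correcting.
7. **Are completers affected?** Not by the permission, which needs an ETV. The scope of Appendix 6 ends with the treatment phase, but the end of a list's scope does not grant permission, so section 6.5.2 can stand beside it.
8. **Can the interval be put in weeks?** Section 1.1 gives a 73-week maximum, up to 5 weeks of screening, 12 weeks of induction and 40 weeks of maintenance: 73 − 5 − 12 − 40 = 16 weeks. That is an implied follow-up for someone who uses the full screening window and completes treatment. Such a person is outside the permission. Follow-up timing for early discontinuers is redacted, so no figure can be given for the affected group.
9. **How many people?** SAP section 3 reports 6 enrolled. The documents do not say how many stopped early. The range is 0 to 6.

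**The case against.** The best defence is that a sensible reader would not be misled. The vaccination paragraph is a dedicated rule, the appendix sentence is a general one, and the unreadable cell may carry a specific restriction. The general sentence was probably written with Crohn's disease treatments in mind. Exclusion criterion [24] already keeps out anyone who intends to receive BCG during the study, and section 6.5.2 requires a vaccine-record review at screening. BCG in follow-up would therefore be unusual.

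Much of this stands as a limit on size. It does not remove the conflict, because the protocol states no order of precedence and the permission is written without exception. Criterion [24] governs entry and does not settle what applies after the ETV.

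A reader might also infer more than the documents support:

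- **That live attenuated vaccines are in the same position.** They share the table row, but their period in section 6.5.2 is redacted, so a post-drug prohibition cannot be shown.
- **That all 6 participants face 16 weeks of conflicting rules.** Six is the enrolled cohort, and 16 weeks belongs to completers, who have no ETV.
- **That infection data would be distorted.** SAP section 5.6.7 limits listings of events of special interest to the treatment period by default. Follow-up safety data are listed (SAP 5.6), and adverse events are also summarised over treatment plus follow-up (SAP 5.6.2). With 6 participants and concomitant medications recorded (protocol 6.5), a vaccine dose could be read beside any event. Harm to the analysis is speculation.
- **That section 6.5.2 should prevail.** It gives no reason for its restriction, and choosing the rule is a medical decision.

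**Conclusion.** The inconsistency is real and can be seen in the unredacted text. For early discontinuers between the ETV and the end of follow-up, one passage permits BCG and another prohibits it. The finding rests on reading the Appendix 6 permission as covering every row of its table, and on follow-up being part of the study, which section 4.1 states. It does not rest on any redacted duration.

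Its size is small: BCG only, early discontinuers only, somewhere between none and 6 people, over an interval whose length is not public. Efficacy estimates are unaffected. It deserves correction because it concerns a participant-safety instruction. The documents do not say whether anyone is still in the affected interval, so its practical weight cannot be judged further.

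**What to change.** Reconcile the opening text of Appendix 6 with the vaccination text of section 6.5.2, so that a single vaccine rule for the time after study drug is stated identically in both places. The sponsor's medical team decides what that rule is, how long it runs, and how it treats live attenuated vaccines. While doing so, the team should check that the guidance cell for the vaccine row agrees with the result.

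The cost is a sentence or so of text, issued as a protocol clarification or a letter to sites. No visit, test, data item or analysis changes.
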